### **9.2.2. Cohort Study**

#### **9.2.2.1. Inclusion Criteria**

Patients must meet all of the following inclusion criteria to be eligible for inclusion in Phase 2 of the study:

1. Age  $\geq$  6 months on the day of receiving their first recorded dose of the COMIRNATY 2023-2024 Formula (if a vaccine recipient), or on the day they experience a healthcare encounter (if a comparator), defined as the cohort entry date (Section 9.2.3).
2. Have continuous medical and pharmacy insurance coverage in the 365 days prior to the cohort entry date, or since birth if the cohort entry date occurred at  $<$  1 year of age.

#### **9.2.2.2. Exclusion Criteria**

Patients meeting any of the following criteria will not be included in Phase 2 of the study:

1. Are of unknown sex.
2. Have a missing month and year of birth.
3. Have received a COVID-19 vaccine in the 270 days prior to cohort entry date (as defined in Section 9.2.3).
4. Have received both the COMIRNATY 2023-2024 Formula and a COVID-19 vaccine other than the COMIRNATY 2023-2024 Formula on the cohort entry date (defined in Section 9.2.3).

In both phases of the study, when creating the analytic population for each specific safety outcome of interest, individuals will be excluded if they experienced that safety outcome during the portion of the baseline period designated as the clean period ([Section 9.2.4](#)).

### **9.2.3. Vaccination Date and Cohort Entry Date**

In the Phase 1 SCRI analysis, the date of first vaccination with the COMIRNATY 2023-2024 Formula will be set as the vaccination date. For the analysis assessing individuals who receive more than one dose of the COMIRNATY 2023-2024 Formula, each vaccination with the COMIRNATY 2023-2024 Formula will be set as a new vaccination date.

In the Phase 2 cohort analysis, the cohort entry date will be the date individuals in the COMIRNATY group receive their first recorded dose of the COMIRNATY 2023-2024 Formula. For individuals in the comparator cohort, the cohort entry date will be set as the date of first qualifying healthcare encounter. Propensity score-matched comparators will also be matched on age group and calendar time. Regarding age, matching will be performed between patients within age groups (e.g., 6 months–4 years, 5–11 years, 12–17 years, 18–64 years, and  $\geq 65$  years). Regarding calendar time, patients will be matched within 14-day windows (e.g., 01 September 2023 to 14 September 2023, 15 September 2023 to 28 September 2023) in which individuals in the exposed cohort will have received vaccination with the COMIRNATY 2023-2024 Formula and individuals in the unexposed cohort will have had a healthcare encounter but no recorded vaccination with the COMIRNATY 2023-2024 Formula. Alternate calendar periods (e.g., one month) may be empirically explored.

For matched comparators, the cohort entry date will be the date within the matched 14-day calendar period on which they had a healthcare encounter.

#### **9.2.4. Baseline Period**

The baseline period will consist of all continuously enrolled available time up to one year (365 days) prior to the vaccination date (SCRI) or cohort entry date (cohort study). Recognizing that narrower or specific windows of assessment may better capture select patient attributes of interest, specific covariates may be assessed using alternate time period(s). In this study, all individuals are required to have a minimum of 365 days of continuous health plan enrollment prior to the vaccination or cohort entry date (Sections 9.2.1.1 and 9.2.2.1), or continuous enrollment since birth if the vaccination or cohort entry date occurred at  $< 1$  year of age.

In both study designs, some or all of the baseline period will be used to exclude individuals with prevalent outcomes prior to vaccination or cohort entry date. This portion of the baseline period will be referred to as the ‘clean period.’ For a list of outcome-specific clean periods, please see [Section 9.3.2](#).

#### **9.2.5. Follow-Up Period**

##### **9.2.5.1. SCRI**

In the SCRI analysis, follow-up for the risk period will begin upon (for the outcomes of anaphylaxis and convulsions/seizures) or one day after (for all other outcomes) receipt of the COMIRNATY 2023-2024 Formula ([Table 2](#)) and continue until the earliest of:

- Receipt of a COVID-19 vaccine other than the COMIRNATY 2023-2024 Formula;
- The end of the outcome-specific risk interval as defined in [Section 9.3.2](#);
- Disenrollment from the health plan, death, or the end of data collection.

After the outcome-specific pre-specified washout period following the risk interval, follow-up for the control period will begin and continue until the earliest of:

- Receipt of a COVID-19 vaccine other than the COMIRNATY 2023-2024 Formula;
- The end of the control period as defined in [Section 9.3.2](#);
- Disenrollment from the health plan, death, or the end of data collection.

Individuals will be followed for each safety outcome during both the risk and control periods, such that events observed during the risk period or washout period will not censor follow-up for the control period.

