#### 9.1.1. SCRI

Phase 1 will monitor the incidence rate of pre-specified safety events of interest in a general population of individuals who receive the COMIRNATY 2023-2024 Formula using an SCRI study design that tracks post-vaccination risk intervals and control (reference) periods for each vaccinated individual. Monitoring will be conducted during a pre-specified risk period immediately following vaccination, and the observed rate of events during this risk period will be compared to that of a control period temporally removed from the vaccination event. As depicted in [Figure 1](#), only individuals who receive the COMIRNATY 2023-2024 Formula will be included in the SCRI study ([Baker et al., 2015](#)). Within each individual, outcomes occurring during the risk interval will be compared with those occurring during the control period, in order to determine whether these outcomes occur more frequently immediately after vaccination as compared with a reference period. A washout period may be inserted between the risk interval and the control period to ensure that events relating to the vaccine are not incorrectly attributed to the control period. To ensure that observed outcomes are truly incident, a period free from the outcome of interest (clean period) may be required prior to vaccination.

090177e1a5be86fe\Approved\Approved On: 19-Mar-2026 15:57 (GMT)

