**Figure 1. Self-controlled risk interval design**

Certain individuals (i.e., immunocompromised patients aged 6 months through 11 years; [FDA, 2023b](#)) may receive more than one dose of the COMIRNATY 2023-2024 Formula and thus may have multiple risk and control periods. For these individuals, analysis may be conducted using the first dose and repeated by pooling the multiple risk periods, as well as the control periods.

The safety outcomes of interest, along with relevant clean windows, risk intervals, and washout and control periods, are listed in [Section 9.3.2](#).

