### 9.3.2.1. Outcome-Specific Risk and Control Periods

The SCRI design ([Section 9.1.1](#)) requires that clean periods, risk intervals, washout periods, and control intervals be specified for every study outcome. The lengths of the clean periods and risk intervals are listed in [Table 2](#). The washout period for all outcomes will begin immediately after the end of the risk interval and continue for 30 days ([Akpandak et al., 2022](#)); the control period will follow the washout period and be equivalent in length to the risk interval. Interval lengths were determined based on prior vaccine literature, including COVID-19 vaccine studies conducted as part of the FDA’s Center for Biologics Evaluation and Research (CBER) Biologics Effectiveness and Safety (BEST) System ([Akpandak et al., 2022](#); [Barda et al., 2021](#); [CBER, 2021](#); [Joy et al., 2023](#); [Klein et al., 2021](#); [Liu et al., 2023](#); [Martin et al., 2021](#); [McCarthy et al., 2013](#); [Wack et al., 2021](#)).

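### First-dose SCRI control time is not adjusted for a later COMIRNATY 2023-2024 dose, so in the few multi-dose recipients dose-2 risk days can be counted as control days

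*Protocol*

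**What the plan says.** - **Follow-up (Section 9.2.5.1).** The lists for the risk period and the control period both open with "Receipt of a COVID-19 vaccine other than the COMIRNATY 2023-2024 Formula". The other stops are the end of the window, disenrollment, death and the end of data collection. A repeat dose of the study vaccine appears in neither list.
- **Repeat doses (Section 9.1.1, text under Figure 1).** Certain people "may receive more than one dose of the COMIRNATY 2023-2024 Formula and thus may have multiple risk and control periods". One group is named, with i.e. rather than e.g.: immunocompromised children from 6 months to 11 years. For them, "analysis may be conducted using the first dose and repeated by pooling the multiple risk periods, as well as the control periods".
- **Index date (Section 9.2.3).** For the main analysis, "the date of first vaccination with the COMIRNATY 2023-2024 Formula will be set as the vaccination date". For the multi-dose analysis, "each vaccination with the COMIRNATY 2023-2024 Formula will be set as a new vaccination date".
- **Windows (Section 9.3.2.1).** "The washout period for all outcomes will begin immediately after the end of the risk interval and continue for 30 days"; then "the control period will follow the washout period and be equivalent in length to the risk interval".
- **Purpose of the washout (Section 9.1.1).** It is there "to ensure that events relating to the vaccine are not incorrectly attributed to the control period".

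**The concern.** Read together, these sections keep a multi-dose recipient in the first-dose analysis with the control window still running after dose 2. Days at risk from dose 2 then serve as unexposed reference time, which is what the washout is meant to prevent. Section 9.2.5.1 ends control time at another manufacturer's vaccine but not at a repeat of the product under study, which is the more direct source of contamination.

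No other section closes the gap. The 270-day exclusion in Section 9.2.1.2 looks back from the vaccination date, so it does not remove someone whose second dose comes later. The pooled analysis is an optional repeat and leaves the first-dose estimate unchanged. Section 9.7.1.1 has no rule for overlapping windows. Section 7 calls the document a combined protocol and statistical analysis plan, and Annex 1 lists no standalone documents, so the rule has not visibly been left to another text.

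In a safety study the error, where it occurs, runs toward missing an effect.

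**Working it through.** The Protocol states no figure on this point, so there is none to reproduce.

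**Inputs.** Risk interval from day s to day e, of length L = e − s + 1 (Table 2); a 30-day washout and a control window of length L (Section 9.3.2.1). Assumed, because not given: dose 2 on day d, true rate ratio r = 3 after each dose, and the share of people affected.

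**Windows.** Control time runs from day e + 31 to day e + 30 + L. The dose-2 risk interval runs from d + s to d + e. They share at least one day when d + e ≥ e + 31 and d + s ≤ e + 30 + L, that is, when 31 ≤ d ≤ e + 30 + L − s.

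| Risk interval | L | Control window | Dose-2 days giving overlap | Full overlap at d |
|---|---|---|---|---|
| Days 0–1 (anaphylaxis) | 2 | 32–33 | 31–33 | 32 |
| Days 0–21 (ADEM, seizures) | 22 | 52–73 | 31–73 | 52 |
| Days 1–21 (e.g. myocarditis/pericarditis) | 21 | 52–72 | 31–71 | 51 |
| Days 1–28 (e.g. myocardial infarction) | 28 | 59–86 | 31–85 | 58 |
| Days 1–30 (herpes zoster) | 30 | 61–90 | 31–89 | 60 |
| Days 1–42 (e.g. Guillain-Barré syndrome) | 42 | 73–114 | 31–113 | 72 |

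A second dose on or before Day 30 never reaches control time.

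**Within affected people.** Let o be the number of control days inside the dose-2 risk interval. For intervals starting on Day 1, o is the smaller of d − 30 and 2L + 30 − d, and zero outside the range above. The expected reading is

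RR = rL / [(L − o) + r·o], which for r = 3 is 3L / (L + 2o).

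| Dose 2 on day | L = 42 | L = 28 | L = 21 |
|---|---|---|---|
| 42 | o = 12: 126/66 = 1.91 | o = 12: 84/52 = 1.62 | o = 12: 63/45 = 1.40 |
| 56 | o = 26: 126/94 = 1.34 | o = 26: 84/80 = 1.05 | o = 16: 63/53 = 1.19 |
| 60 | o = 30: 126/102 = 1.24 | o = 26: 84/80 = 1.05 | o = 12: 63/45 = 1.40 |
| 77 | o = 37: 126/116 = 1.09 | o = 9: 84/46 = 1.83 | o = 0: 3.00 |
| 90 | o = 24: 126/90 = 1.40 | o = 0: 3.00 | o = 0: 3.00 |

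At full overlap the reading is 1.00. At the edge of the range (o = 1, L = 42) it is 126/44 = 2.86.

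**All recipients.** If a share f of people is affected and a share w = o/L of their control time overlaps, RR = r / [1 + f·w·(r − 1)]. With r = 3 and w = 1:
- f = 0.1%: 3/1.002 = 2.99
- f = 1%: 3/1.02 = 2.94
- f = 5%: 3/1.10 = 2.73

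This takes the baseline rate as equal in affected and other recipients. If it differs, f becomes the affected people's share of expected baseline events for that outcome.

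**Pooled repeat.** Take two doses per person, all affected, a clean dose-2 control window and L = 42. Then RR = 2Lr / [(2L − o) + r·o], which for r = 3 is 252 / (84 + 2o): 2.33 at d = 42, 1.75 at d = 60 and 1.50 at d = 72. The same calendar day is then both dose-2 risk time and dose-1 control time.

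**With overlapping days removed.** For L = 42 and d = 60, dose-2 risk covers Days 61–102, so control Days 103–114 remain (12 days). The reading is (3 × 42/42) / (12/12) = 3.00.

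**The case against.** The strongest reply is that the effect is confined and unproven. Section 9.1.1 names one small group. Phase 1 plans no SCRI subgroup by age or immune status; those subgroups belong to the Phase 2 cohort (Section 9.7.2.4). The Protocol gives no dose interval, so overlap cannot be shown to occur, and there is no bias if the true RR is 1. All of this stands, and it limits the size of the problem. It does not supply the missing rule.

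A reader might infer that the all-recipient RR is pulled well down, say from 3 to between 2.7 and 1.5, and that the signal rule in Section 9.3.2 (RR above 3.0 with P below 0.01) is compromised. The documents do not support that. It would need about 5% to 50% of all control time to be contaminated. With 1% affected and full overlap, the true RR at which the estimate reads 3 solves r = 3[1 + 0.01(r − 1)], so r = 2.97/0.97 = 3.06. Outcomes seen mainly in children, such as Kawasaki disease, could be affected more, but nothing in the Protocol lets that be sized.

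A second reply is that multi-dose recipients have their own repeat analysis. It is optional and lacks an overlap rule. In addition, 11 September 2023 to 31 March 2024 spans 202 days. If the 270-day exclusion were applied at each new vaccination date, every second dose in that span would drop out of the repeat. The two provisions need reconciling.

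A third concerns the remedy. Ending follow-up at any later dose looks simple, but it deletes clean control windows when dose 2 falls by Day 30 and leaves no control time whenever dose 2 precedes the control window. If an event after dose 1 deters dose 2, it could also discard control events selectively and raise the RR. That objection is sound and shapes the fix below.

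**Conclusion.** The omission is real and no other section repairs it. Followed as written, the plan can count dose-2 risk days as dose-1 control days when dose 2 falls in the ranges tabulated. The bias is toward 1, provided that the true RR exceeds 1 and dose 2 has a similar effect.

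It is heavy within affected people: a true RR of 3 reads 1.0 to 1.9 at most overlapping spacings, and closer to 3 only when few days overlap. It is small for the all-recipient estimate: about 2.99 at 0.1% affected and 2.94 at 1%, with full overlap. These sizes rest on assumed spacing, assumed shares and equal baseline rates. The point is worth correcting because it contradicts the stated purpose of the washout and the correction is cheap. It does not show that the primary SCRI result is materially wrong.

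**What to change.** In Section 9.2.5.1, exclude from dose-1 control person-time and control events any day that lies in the outcome-specific risk interval of a later COMIRNATY 2023-2024 dose. Let the person-time offset in Section 9.7.1.1 reflect the days that remain, and state that people with no control time left contribute no comparison. Apply the same overlap rule to the pooled multi-dose repeat in Section 9.1.1, and say how the 270-day exclusion applies there. Report, by outcome, the number of people and control days affected; this also replaces the assumed shares with observed ones.

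The cost is a short text change, some programming and slightly less control time in a few multi-dose cases. Clean control windows are kept when dose 2 comes by Day 30, and usable days are kept in cases such as the 42-day interval with dose 2 on Day 60, where 12 control days survive.

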**Table 2. Clean periods and risk intervals for safety outcomes of interest**

Outcome	Clean Period*	Vaccine Risk Interval*	Care Setting**
Acute disseminated encephalomyelitis	Days -28 to -1	Days 0 to 21	IP
Anaphylaxis	Days -30 to -1	Days 0 to 1	IP, ED
Bell's palsy	Days -183 to 0	Days 1 to 42	IP, OP
Cerebral venous sinus thrombosis	Days -365 to 0	Days 1 to 28	IP, OP
Convulsions/seizures, non-febrile	Days -42 to -1	Days 0 to 21	IP, OP
Encephalomyelitis	Days -183 to 0	Days 1 to 42	IP
Glomerulonephritis	Days -365 to 0***	Days 1 to 42***	IP, OP
Guillain-Barré syndrome	Days -365 to 0	Days 1 to 42	IP-primary position only
Herpes zoster	Days -270 to 0	Days 1 to 30	IP, OP
Immune-mediated myositis	Days -365 to 0***	Days 1 to 28	IP, OP
Immune thrombocytopenia	Days -365 to 0	Days 1 to 42	IP, OP
Kawasaki disease	Days -365 to 0	Days 1 to 21	IP, OP
Multi inflammatory syndrome	Days -365 to 0	Days 1 to 42	IP, ED
Multiple sclerosis	Days -365 to 0	Days 1 to 42***	IP, OP
Myocardial infarction	Days -365 to 0	Days 1 to 28	IP
Myocarditis/pericarditis	Days -365 to 0	Days 1 to 21	IP, OP

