## 9.7. Data Analysis

### 9.7.1. SCRI

#### 9.7.1.1. Primary Analysis

Descriptive statistics will be used to summarize the baseline characteristics of those who receive the COMIRNATY 2023-2024 Formula. Counts of each safety outcome of interest will be reported within pre-specified risk and control windows. Then, the observed incidence rates of the outcomes of interest will be estimated in the risk window and the control window. Among the individuals who experience an outcome of interest in either the risk window or the control window (but not both), an exact conditional Poisson regression model with the natural logarithm of the person-time as the offset will be used to calculate the relative incidence (rate ratio) and corresponding 95% confidence interval (CI) of the risk period relative to the control period. With the self-controlled design, whereby each individual serves as their own comparator, the analysis accounts for the factors that vary across but not within individuals (i.e., time-invariant covariates).

The results from the SCRI utilizing the Optum pre-adjudicated claims database will be presented in the interim report, while results from the SCRI utilizing the ORD will be presented in the final report.

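### Stopping SCRI person-time at death removes early-fatal risk-window cases from the conditional rate ratio and biases it downward for outcomes with early deaths

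*Protocol*

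**What the plan says.** Protocol 9.2.5.1 lists the events that end SCRI follow-up. The same item, "Disenrollment from the health plan, death, or the end of data collection", stands in the list for the risk period and in the list for the control period. On the control period it says: "After the outcome-specific pre-specified washout period following the risk interval, follow-up for the control period will begin and continue until the earliest of" the listed stops. It adds that "events observed during the risk period or washout period will not censor follow-up for the control period". That exempts the event itself. It does not exempt a death that follows.

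Section 9.3.2.1 fixes the layout: "The washout period for all outcomes will begin immediately after the end of the risk interval and continue for 30 days", and "the control period will follow the washout period and be equivalent in length to the risk interval". There is no control window before vaccination. Table 2 gives a risk interval of days 1 to 28 for MI, PE, cerebral venous sinus thrombosis and both strokes.

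Section 9.7.1.1 takes people with an event in one window but not both, and fits "an exact conditional Poisson regression model with the natural logarithm of the person-time as the offset". Each person is their own comparator. Section 9.3.2 defines a safety signal as a rate ratio above 3.0 with P below 0.01 in this analysis.

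Section 7 calls the document a combined protocol and SAP, so these are the stated rules and not placeholders for a later plan.

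**The concern.** The conditional model assumes that how long a person is observed does not depend on having the event. Death caused by the event breaks that assumption, and a control window that always lies after the risk window makes the damage one-sided. Early-fatal cases in the risk window lose their comparison time altogether. Early-fatal cases in the control window keep their full risk time.

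What is at stake is the Phase 1 effect estimate and the signal rule built on it. Both would lean towards no harm, most of all for the outcomes that kill early.

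**Working it through.** **Inputs from the Protocol.** Risk interval 28 days (Table 2: MI, PE, both strokes); washout 30 days and equal-length control window (9.3.2.1); person-time stopped at death (9.2.5.1); log person-time as offset (9.7.1.1); signal if the rate ratio exceeds 3.0 and P is below 0.01 (9.3.2).

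**Assumed.** Case fatality *f* and time from event to death; the Protocol gives neither. It also states no event count or power figure to reproduce.

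**1. Layout.** Risk is days 1–28, washout days 29–58, control days 59–86. A risk-window case who dies by day 58 has control time T0 = 0.

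**2. Likelihood of one case.** With risk time T1 and control time T0, the probability that the event falls in the risk window is RR·T1 / (RR·T1 + T0). If T0 = 0 this is 1 for every RR (checked at 0.5, 1, 3 and 10), so the case carries no information. As an offset, ln(0) is undefined.

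**3. Two examples.**
- MI on day 5, death on day 10: T1 = 10, T0 = 0. The case leaves the estimate.
- MI on day 65, death on day 70: T1 = 28, T0 = 70 − 58 = 12. The case stays. At RR = 1 its expected share in the risk window is 28/(28 + 12) = 0.70 instead of 0.50, so a control-window event counts more heavily against a raised risk.

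**4. Size.** If a fraction *f* of risk-window cases drops out and nothing else happens, the estimate is RR × (1 − *f*). Shortened control time pulls it lower still. Simulation with 28/30/28-day windows and death within 7 days of the event gives:

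| True RR | f = 5% | 10% | 20% | 30% |
|---|---|---|---|---|
| 1.0, drop-out only | 0.95 | 0.90 | 0.80 | 0.70 |
| 1.0, as written | 0.94 | 0.87 | 0.75 | 0.63 |
| 2.0, as written | 1.87 | 1.77 | 1.53 | 1.31 |
| 3.5, drop-out only | 3.33 | 3.15 | 2.80 | 2.45 |
| 3.5, as written | 3.29 | 3.11 | 2.72 | 2.34 |

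Solving the score equation directly, without simulation, agrees to within about 0.02.

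**5. Other assumptions.** With exponential time to death (mean 5 days), a true 4.0 becomes 3.57 at 10% and 3.13 at 20% fatality. With planned window lengths it is recovered as 4.00. Section 9.7.1.1 does not name the stratum variable. If person-time were pooled over cases, a true 3.5 would still fall to 3.07 at 20% and 2.84 at 30%.

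**6. Signal rule (assumed counts, exact two-sided test at 0.5).**
- 20 risk against 5 control: RR 4.0, P = 0.0041, a signal.
- Two of the 20 die before control time opens: 18 against 5, RR 3.6, P = 0.0106, no signal.
- 40 against 10: RR 4.0, P = 0.00002. Lose 12: 28 against 10, RR 2.8, no signal.

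**The case against.** A reader might infer that the study hides fatal events. The Protocol does not support that. Section 9.7.1.1 also reports counts and incidence rates by window, and fatal cases stay in both. The Phase 2 cohort counts an event when it occurs, so a later death cannot remove it, and 9.1 presents the two designs as complementary. None of this corrects the Phase 1 rate ratio.

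A reader might also infer that a real signal would be missed. Section 9.3.2 allows record review for estimates approaching the threshold and for analyses beyond the primary SCRI. Those provisions are optional, so they soften the consequence without removing it. At 5% and 10% fatality a true 3.5 also stays above 3.0.

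The size rests on assumed fatality. Outcomes such as Bell's palsy or herpes zoster would barely be affected.

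Two practical points stand. Sections 9.4.1 and 9.4.2 describe enrolment and claims but no source of death dates, so a death seen only as disenrollment would still be truncated under a rule that exempts death alone. And version 3.0 is dated 18 March 2026, after the planned interim report of 30 June 2024 and shortly before the final report planned for 30 April 2026. Dropping the existing rule outright would break comparability with the interim.

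**Conclusion.** The bias follows from stated rules, always runs downward, and is neither repaired elsewhere nor listed in 9.9. It is confined to the SCRI rate ratio and the signal rule that uses it, and it matters for outcomes with deaths before the control window opens. Under assumed fatality of 5% to 30%, 28-day windows and death within 7 days, a true 1.0 is estimated as about 0.94 to 0.63 and a true 3.5 as about 3.3 to 2.3. The direction holds under either reading of the conditioning; the size is only as good as the fatality assumption. The Protocol does not support the stronger claims that fatal events vanish from the study or that a signal is bound to be lost.

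**What to change.** In 9.2.5.1 and 9.7.1.1, for the final-report SCRI:

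- Use the planned window lengths as the offset for cases who die after the event, at least as a sensitivity analysis.
- Do the same for cases whose enrolment ends soon after the event, where death cannot be told from disenrollment. Define that interval in advance.
- Report the death-truncated result alongside, for comparability with the interim report.
- Give, per outcome, the number of risk-window cases with no control time.
- Add the limitation to 9.9.

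**Cost.** A short text change and one more run of the same model. The drawback is a small upward bias, because people who die of other causes between the windows cannot become control cases. The windows start 58 days apart for 28-day outcomes (28 + 30) and 72 days apart for 42-day outcomes (42 + 30). With annual mortality *m*, the bias is (1 − *m*)^(−days/365) − 1. At *m* = 1% that is 0.16% to 0.20%. At *m* = 10% it is 1.7% to 2.1%. It passes 1% once annual mortality among people at risk of the event exceeds about 5% to 6%, so it should be stated and not assumed negligible.
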